PRO 140 525mg	Parenteral solution	175 mg/mL	2 injections of PRO 140 (2 X 1.5 mL/inj.) for remainder of treatment phase	SC injection										
PRO 140 700mg	Parenteral solution	175 mg/mL	2 injections of PRO 140 (2 X 2 mL/inj.) for remainder of treatment phase	SC injection										

Name of Sponsor: CytoDyn, Inc.	
Name of Study Product: PRO 140 (Humanized monoclonal antibody to CCR5)	
Protocol Number: PRO 140_CD03	Indication: Human Immunodeficiency Virus Type-1 (HIV-1) Infection
of physical examinations, as detailed in the schedule of procedures and assessments of the protocol.	
Follow-up Phase: Duration of Follow-up Phase is determined based on whether or not subject has experienced virologic failure during the Treatment Phase. 
 
Group A or Group B subjects not participating in Part 2 and Group C subjects who experience virologic failure during the Treatment Phase will be assessed every 4 weeks until the viral suppression is achieved (i.e., plasma HIV-1 RNA levels decline to < 50 copies/mL). Additionally, virologic failure subjects will return to clinic for long-term follow-up at 6 months and at one year from the time of the Virologic Failure (VF) Visit.
 
Subjects who do not experience virologic failure and complete Treatment Visit 48 (T48), will be assessed every 2 weeks for total of 4 weeks.
 
	
Duration of Treatment: 
 
Screening Phase: up to 6 weeks
 
Treatment Phase: 48 weeks ± allowed windows (up to 48 treatments every week (±3 days)).
 
Follow-up Phase: 
 
Virologic Failure: Until viral suppression is achieved. Additionally, subjects who experience virologic failure will return to clinic for long-term follow-up at 6 months and at one year from the time of the Virologic Failure Visit.
 
Non-Virologic Failure (NVF): 4 weeks
 
 
 
	
Total Study Duration: 58 weeks [Does not include additional long-term follow-up time for virologic failure subjects]	

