**Figure 3-1: Study Flow Diagram**

## 4 STUDY SCHEDULE

The study is divided into three phases: Screening, Treatment and Follow-up.

(1) **Screening Phase** (Screening to T1 Visit) begins with signing of Informed Consent and lasts up to 6 weeks. Subject will enter the Treatment Phase as soon as HIV-1 viral tropism results are available for review by Investigator.

**Treatment Phase** (T1 to T48 Visit) begins with Treatment Phase begins with an evaluation of results of laboratory samples collected at the Screening Visit. The first treatment (T1) visit will be administered within 42 days of the Screening Visit, with weekly visits ( $\pm 3$  days) thereafter. The first 300 eligible subjects were randomized 1:1 to receive either PRO 140 350mg weekly (Group A) or PRO 140 525mg weekly (Group B). Once the enrollment of 300 subjects was completed, additional subjects will be randomized 1:1 to PRO 140 525mg (Group B) or PRO 140 700mg (Group C).

All subjects will continue taking their existing ART during the Screening Phase and for first week of the Treatment Phase. After Week 1 of the Treatment Phase, subjects will stop their existing ART regimen and receive assigned dose of PRO 140 SC monotherapy.

Study participants will be regularly monitored for viral load following initiation of PRO 140, and will cease weekly study treatment injections should they experience virologic failure.

Subjects who experience virologic failure at any point during Part 1 of Treatment Phase will undergo the Virologic Failure (VF) Visit assessments and then exit the Treatment Phase to enter the Follow-up Phase of the study. unless subjects in Group A opt to enter Part 2 of Treatment Phase and receive PRO 140 525mg SC weekly injections or subjects in Group B opt to enter Part 2 of Treatment Phase and receive PRO 140 700mg SC weekly injections for remainder of 48-week Treatment Phase.

Subjects who do not experience virologic failure will enter the Follow-up Phase of the study at the end of 48-week Treatment Phase.

(2) **Follow-Up Phase:** The duration of follow-up depends on the status of viral load suppression.

- Subjects who experience virologic failure will be followed up every 4 weeks until viral suppression is achieved (i.e., plasma HIV-1 RNA levels to return to  $< 50$  copies/mL). Additionally, virologic failure subjects will return to clinic at 6 months and at one year from the time of the Virologic Failure (VF) Visit.

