**Table 4-2: Schedule of Assessments –Treatment Phase (T17 – T48)**

Procedure/Assessments	Treatment Phase (T17 – T48)											In case of Treatment Failure	
	Visit	T17	T18-21	T22-25	T26-29	T30-33	T34-37	T38-41	T42-45	T46	T47		T48
Window Period	±3 days since last treatment												
Physical Examination	X 	X 	X 	X 	X 	X 	X 	X 	X 	X 	X 	X	X
Neurological Assessment 												X	X
Vital Signs 	X	X	X	X	X	X	X	X	X	X	X	X	X
ECG												X	X
Complete Blood Count (CBC) 			X				X					X	X
Biochemistry 			X				X					X	X
Coagulation Indices			X				X					X	X
Urinalysis			X				X					X	X
Plasma HIV-1 RNA level 	X	X	X	X	X	X	X	X	X			X	X
TruCount T assay 	X	X	X	X	X	X	X	X	X			X	X
Trofile® DNA Assay												X	X 
Trofile® RNA Assay													X 
HIV-1 Drug Resistance Assay 												X	X
PRO 140 Administration – Group A (350mg SC) – Group B (525mg SC) – Group C (700mg SC)	X	X	X	X	X	X	X	X	X	X	X	X	
Combination ART Regimen 											X	X	X
Injection Site Reaction Assessment 	X	X	X	X	X	X	X	X	X	X	X	X	
Injection Site Pain Assessment (VAS) 	X	X	X	X	X	X	X	X	X	X	X	X	
PK sample for PRO 140 		X		X			X		X			X	X
Anti-idiotypic antibodies to PRO 140 		X		X			X		X			X	X
Measurement of treatment adherence 		X	X	X	X	X	X	X	X	X	X	X	X
Adverse Events	X	X	X	X	X	X	X	X	X	X	X	X	X
Concomitant Medications	X	X	X	X	X	X	X	X	X	X	X	X	X
Potential Biomarkers													
Immune Activation Markers 												X	X
PhenoSense® Entry Assay 												X	X
Quest Diagnostics Tropism Assay 													X

Procedure/Assessments	Treatment Phase (T17 – T48)											In case of Treatment Failure
	Visit	T17	T18-21	T22-25	T26-29	T30-33	T34-37	T38-41	T42-45	T46	T47	
Window Period	±3 days since last treatment											
CNS sub-study (n=20)												
CSF sample collection 												X
GU sub-study (n=20)												
Genital Secretion sample collection 												X
CCR5 Receptor Occupancy 	X	X	X	X	X	X	X	X	X	X	X	X
CCR5 Genotyping 											X	X

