**Foot Notes:**

- [1] Symptom-directed physical examination at clinic visits.
- [2] The neurological assessment tool is based on the three question survey used by Simioni et al. (Simioni S, 2010). Additional neurological assessment modalities may be used as per Investigator's discretion.
- [3] Post treatment vital signs (blood pressure, heart rate, respiration rate, and temperature) will be measured at clinic visit.
- [4] Hemoglobin, Hematocrit (HCT), Red Blood Cells (RBC), White Blood Cells (WBC) with total and differential count, Absolute Neutrophil Count (ANC) and platelets.
- [5] Serum Biochemistry  
 Hepatic function indicators: total and direct bilirubin, alkaline phosphatase, aspartate aminotransferase (AST), alanine aminotransferase (ALT), total protein, Lactate dehydrogenase (LDH)  
 Renal function indicators: BUN, creatinine  
 Electrolytes: sodium, potassium, chloride, calcium and bicarbonate  
 Other: glucose (random), cholesterol (total)
- [6] Blood sample for plasma HIV-1 RNA level collected at least once every four weeks between T18-21, T22-25, T26-29, T30-33, T34-37, T38-41 and T42-45 visits when subject comes to clinic.
- [7] Blood sample for TruCount T assay collected at least once every four weeks between T18-21, T22-25, T26-29, T30-33, T34-37, T38-41 and T42-45 visits when subject comes to clinic. Assay includes: Absolute Lymphocytes, CD3 cell count, CD4 cell count, CD8 cell count, CD3%, CD4% and CD8%
- [8] Monogram Biosciences GenoSure Archive Assay will be performed at T48 visit. PhenoSense® GT (and PhenoSense Integrase and GeneSeq Integrase testing, if applicable), will be performed at the time of virologic failure.
- [9] Study subjects will re-initiate their previous antiretroviral regimen or an alternative regimen selected by their treating physician: (1) One week prior to the end of 48-week Treatment Phase, or (2) Anytime during the Treatment Extension Phase, if virologic failure occurs or have met any other criteria for discontinuation of study treatment as specified in the protocol.
- [10] Injection Site Reaction Assessment as assessed by Investigator (or designee) at the clinic visits and by visiting nurse or qualified medical professional during home visits. Injection Site Reaction Assessment will not be applicable if PRO 140 is self-administered by subjects at home.

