**Table 4-6: Part 2: Single-Arm, Open-label Treatment Phase [Group B]**

Study Drug	Dosage Form	IP concentration	Dosing Frequency and Amount	Route of Administration
PRO 140 700mg	Parenteral solution	175 mg/mL	2 injections of PRO 140 (2 X 2 mL/inj.) up to Week 48	SC injection

Group A or Group B subjects that do not elect to participate in Part 2 of Treatment Phase and all Group C subjects who experience virologic failure (defined as two consecutive HIV-1 RNA levels of  $\geq 200$  copies/mL) at any time during the Treatment Phase will undergo the Virologic

Failure (VF) Visit assessments and then exit the Treatment Phase to enter the Follow-up Phase of the study.

Subjects who do not experience virologic failure will enter the Follow-up Phase of the study at the end of 48-week Treatment Phase.

All study subjects will re-initiate their previous antiretroviral regimen or an alternative regimen selected by their treating physician:

- One week prior to the end of 48-week Treatment Phase, or
- Anytime during the Treatment Phase, if virologic failure occurs or have met any other criteria for discontinuation of study treatment as specified in [Section 5.2.1](#) of the protocol. Subjects will be allowed to continue PRO 140 monotherapy while waiting for new ART regimen to be constructed by the Investigator.

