#### 4.2.3 Treatment Phase: Treatment Visit-17 (T17) to Treatment Visit-48 (T48)

The following assessments will be performed at each visit during the remaining 32 weeks of the Treatment Phase, unless otherwise specified:

- Assess for any Adverse Events and changes in Concomitant medications (see [Section 9](#) and [7.5](#)),
- Symptom-directed physical examination (see [Section 7.6](#)),
  - **Note:** *Complete physical examination at T48*
- Neurological Assessment (see [Section 7.8](#)) [*occurs at T48*]
- Vital Signs (see [Section 7.9](#))
  - **Note:** *Post-treatment vital signs will be assessed within 15 minutes following study treatment administration*
- Electrocardiogram (ECG) (see [Section 7.7](#)) [*occurs at T48*]

- Collection of Blood Specimens (see [Section 7.10](#)) for
  - Complete Blood Count at least once every 12 weeks at T22-25, T34-37 and at T48 visits
  - Biochemistry at least once every 12 weeks at T22-25, T34-37 and at T48 visits  
Coagulation Indices [Prothrombin time (PT) and INR] at least once every 12 weeks at T22-25, T34-37 and at T48 visits
  - CCR5 Receptor Occupancy (IncellDx Lab)
  - Plasma HIV-1 RNA level
  - TruCount T Assay
    - **Note:** *Blood sample for plasma HIV-1 RNA level and TruCount T Assay should be collected at T17 and at least once every four weeks between T18-21, T22-25, T26-29, T30-33, T34-37, T38-41, T42-45 and T48 visits when subject comes to clinic.*
  - Trofile® DNA Assay [*occurs at T48*]
  - PK sample for PRO 140
  - Anti-idiotypic antibodies to PRO 140
    - **Note:** *PK and ADA blood sample should be collected at least once every four weeks between T18-21, T26-29, T34-37 and T42-45 visits, and at T48 visits.*
  - HIV-1 Drug Resistance Assay – GenoSure Archive [*occurs at T48*]
  - Blood sample for evaluation of potential biomarkers [*occurs at T48*]
    - Immune Activation Markers
    - PhenoSense® Entry Assay
- Collection of Urine Specimen for Urinalysis (see [Section 7.10.15](#)) at least once every 12 weeks at T22-25, T34-37 and at T48 visits.
- Measurement of treatment adherence (see [Section 7.14](#))
  - **Note:** *At least once every four weeks between T18-21, T22-25, T26-29, T30-33, T34-37, T38-41 and T42-45 visits followed by at T48 and VF visits when subject comes to clinic.*
- Study Treatment Administration (PRO 140)  

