**Note:** All treatment injections must be administered by a qualified medical professional (MD, DO, PA, LPN, LVN, NP, RN or CMA if permitted by state law) at clinic site or

home visit or self-administered by subjects, for the duration of 48 weeks in the Treatment Phase.

- Injection Site Reaction Assessment (see [Section 7.12](#))
  - **Note:** *To assess injection site reactions, the Investigator will use the DAIDS AE grading table (refer to [Section 17.3](#)).*
- Subject-perceived Injection Site Pain Assessment (see [Section 7.13](#))
  - **Note:** *Subject-perceived injection site pain will be assessed using the Pain Visual Analog Scale (VAS) prior to study treatment administration assessing average pain at injection site since last treatment.*
- Re-initiate previous antiretroviral regimen or an alternative regimen selected by the treating physician at Week-47, if viral load remain suppressed.

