#### 7.10.9 Plasma HIV-1 RNA level and TruCount T Assay

- Frequency of testing: At SV, T1, T2, T4, T6, T8, T10, T12, T14, T16 and T17, at least once every four weeks between T18-21, T22-25, T26-29, T30-33, T34-37, T38-41, T42-45, T48 and at VF visits when subject comes to clinic. In addition, blood sample will also be collected at all Virologic Failure Follow-up (VF-FU) Visits or Non-Virologic Failure Follow-up (NVF-FU) Visits.
- To assess antiretroviral therapeutic response to PRO 140 or cART regimen

**Note:** Plasma HIV-1 RNA level will be measured using Human Immunodeficiency Virus 1 (HIV-1), Quantitative, RNA (Taqman® Real-Time PCR) test.

TruCount T Assay includes measurement of Absolute Lymphocytes, CD3 cell count, CD4 cell count, CD8 cell count, CD3%, CD4% and CD8%

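### If ART restarts at T47, the only week-48 HIV-1 RNA is drawn about 7 days into ART, and the SAP has no rule for on-ART values in the week-48, rescue re-suppression or time-to-failure analyses

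*Protocol*

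**What the plan says.** **ART restart.** Section 4.2.3 of the protocol reads "Re-initiate previous antiretroviral regimen or an alternative regimen selected by the treating physician at Week-47, if viral load remain suppressed". In Table 4-2 the row "Combination ART Regimen" is marked at T47, T48 and VF. Footnote 9 to that table gives "1) One week prior to the end of 48-week Treatment Phase", and section 4.2 gives "One week prior to the end of 48-week Treatment Phase, or"; neither names a visit. The synopsis, section 3 and section 7.5.1 describe a one-week overlap of ART and PRO 140 at the end of treatment for subjects without virologic failure.

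**HIV-1 RNA sampling.** Section 4.2.3 says samples "should be collected at T17 and at least once every four weeks between T18-21, T22-25, T26-29, T30-33, T34-37, T38-41, T42-45 and T48 visits". Section 7.10.9 ends the treatment-phase list with "T42-45, T48 and at VF visits when subject comes to clinic". Nothing is scheduled at T46 or T47. A note in section 4.2 allows extra draws at the investigator's discretion. Without virologic failure, the next scheduled sample after T48 is NVF-FU1, two weeks later (Table 4-3).

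**Analysis.** SAP 8.2.2.8 reports the percentage completing 24 and 48 weeks of PRO 140 with HIV-1 RNA <50 copies/mL, at the assigned dose and at assigned plus rescue dose. It names no visit, window or ART status. SAP 7.5.6 accepts any value <50 after failure as re-suppression, and 8.2.2.4 uses that definition for rescue subjects within the Treatment Phase. SAP 7.5.5 runs a completer's time to the last visit.

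**The concern.** The week-48 proportion is a primary efficacy measure of PRO 140 as the sole antiretroviral. A value that a week of combination therapy helped to produce cannot show that. With a T47 restart, two kinds of subject can be counted as suppressed on PRO 140 when they were not:

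- a subject who rebounds at a low level after the T42-45 sample and falls below 50 on ART by T48;
- a rescue-arm subject still on the higher dose at T47 and not yet re-suppressed, who first reads <50 at T48.

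The suppression condition in section 4.2.3 does not close the gap: on the schedule, the latest value available to check it is the one from T42-45. A first value of 200 or more at T48 has its next scheduled check at NVF-FU1, about three weeks into ART, so it may never be confirmed. All of these push apparent success upward. In the time-to-failure analysis, follow-up on ART is added to failure-free time on PRO 140.

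**Working it through.** **1. Visit days.** Visits are weekly from T1, so day(Tk) = 1 + 7(k − 1).
- T47 = 1 + 7 × 46 = day 323; T48 = 1 + 7 × 47 = day 330.
- T48 − T47 = 7 days, or 4 to 10 with the ±3-day window. This reproduces the stated one-week overlap.
- T42-45 precedes T47 by 47 − 45 = 2 to 47 − 42 = 5 weeks.

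**2. The other reading.** The phase runs "T1 to T48 Visit) begins with" the T1 dose, so T48 is only 47 elapsed weeks after T1. The stated total is "58 weeks [Does not include additional long-term follow-up time for virologic failure subjects": 6 + 48 + 4 = 58 counts 48 full weeks, whereas visit spacing gives 6 + 47 + 4 = 57. If the phase ends a week after T48, one week before its end is T48 itself. The T48 sample could then be drawn before the first ART dose.

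**3. What a week of ART could hide.** The documents give no decay rate on ART. Assume single-exponential decay with a half-life h of 1 to 5 days. The highest pre-ART value reading <50 after 7 days is 50 × 2^(7/h):

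| h (days) | copies/mL |
|---|---|
| 1 | 6,400 |
| 2 | 566 |
| 3 | 252 |
| 4 | 168 |
| 5 | 132 |

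A fall from 199 to 50 needs log10(199/50) = 0.60 log10, which 7 days achieves only if h is about 3.5 days or less. Some rebound above 50 is hidden across the whole assumed range; the full 50-199 band is hidden only in part of it.

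**4. Rate of new failure over the gap.** CD01-Extension (protocol 1.4.2.8) had 16 eligible subjects on 350 mg, with failure at ≥400 copies/mL.
- Person-weeks: 5 × 329/7 = 235, plus 37, 140 + 149, 99, 81 + 139, and 5 × 176 to 5 × 198. The total is 1,760 to 1,870.
- Rate: 5/1,870 to 5/1,760 = 0.0027 to 0.0028 per week. 1 − exp(−rate × w) is 0.5-0.6% at w = 2 and 1.3-1.4% at w = 5.
- First year only: 12 of 16 completed a year and one relocated while suppressed, leaving 3 failures. −ln(13/16)/52 = 0.0040 per week gives 0.8% at w = 2 and 2.0% at w = 5.
- Overall: about 0.5 to 2.0 per 100 subjects still failure-free at T42-45. The Poisson 95% limits for 5 events (1.62 to 11.67) give 0.2 to 3.3.

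This takes the extension weeks as running from one common start.

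**5. Weight of one hidden case.** Group A is about 150 + 75 = 225, B about 75 + 100 = 175, C about 100. One case adds 0.44, 0.57 or 1.0 percentage points.

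**6. Time at risk.** NVF-FU2 is four weeks after T48: day 330 + 28 = 358. On-ART days within a completer's time are 358 − 323 = 35 (9.8%) with a T47 restart, or 358 − 330 = 28 (7.8%) with a T48 restart.

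**7. Why the censoring change must apply to everyone.** Take 100 subjects, two with a first value ≥200 at T48 (confirmed later), and a restart at day 323. I use the SAP 7.5.5 formula, which dates failure at the first such value.
- Current rule: 100 at risk at day 330, two events, Kaplan-Meier 98/100 = 0.98.
- Censoring only the 98 non-failures at day 323 and keeping the events at day 330: two at risk, two events, Kaplan-Meier 0.00.
- Ending time at risk at day 323 for all, with the two failures dated there ahead of the censorings: 98/100 = 0.98.

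**The case against.** The overlap is openly stated as part of the design, the analysis is descriptive with no success threshold to cross (SAP 7.3 and 7.4), and all data are listed by subject. ART re-initiation is recorded and summarised (SAP 8.1.5), so on-ART T48 values can be identified afterwards. Higher rebound stays visible at T48, discretionary draws may catch some cases, and week 24 is unaffected. All of this stands and keeps the point small. It does not supply the missing rule: followed as written, the SAP can place on-ART values in the success count.

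The masking is also conditional. A reader might infer that T48 is certainly an on-ART value. Table 4-2 supports that, but the 58-week total allows a T48 restart, so the documents do not settle it.

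A reader might also take 0.5 to 2.0 per 100 as the inflation of the week-48 result. It is not. It counts new confirmed failures at ≥400 copies/mL, from five events on 350 mg, and only some of those would be low enough to be hidden. Conversely, rebound above 50 may be more frequent than failure. The 5-week end also needs a T42 draw with nothing until T48. With strict four-weekly sampling, as in the synopsis, the last draw is T44 or later, the gap to T47 is at most 3 weeks, and the range is about 0.5 to 1.2.

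**Conclusion.** The point holds and is worth fixing, with a modest effect. If ART restarts at T47, the sole scheduled week-48 RNA is drawn 7 days (4 to 10) into ART, and SAP 8.2.2.8 and 8.2.2.4 let that value establish suppression on PRO 140. If the restart is at T48, that masking can disappear. On either reading, SAP 7.5.5 counts 28 to 35 of a completer's 358 days as failure-free while on ART. This lengthens the summarised times; a Kaplan-Meier curve before the restart is unchanged.

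The bias runs towards higher suppression and is probably small. Its size cannot be computed, because the documents give neither the frequency of low-level rebound in the gap nor the decay on ART. They do not support a claim that the week-48 result is invalid, or that the ART timing itself is wrong.

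**What to change.** 1. **Reconcile the restart passages**: when ART restarts (Week-47, one week before the end, T47 in Table 4-2) and who restarts (rescue-arm subjects, and unsuppressed subjects without confirmed failure). This review does not choose the clinical rule.
2. **SAP 8.2.2.8 and 8.2.2.4, all cohorts.** State that an RNA value drawn after the recorded ART restart cannot establish suppression on PRO 140. Take as the end-of-monotherapy result the last value from T42 up to and including the restart day, before the first ART dose, and show its visit. Report the on-ART T48 result as a flagged companion row, and do not count a subject with T48 ≥50 as a success. SAP 8.2.2.6 and 8.2.2.7 stay as they are, since they include re-suppression on ART by design.
3. **Sampling.** For subjects who have not yet reached the restart, draw one RNA sample just before it, at T47, or at T48 if reconciled that way. Report by enrolment cohort.
4. **SAP 7.5.5.** End time at risk at ART restart for every completer, whatever the later results. A failure whose first value ≥200 comes after restart still counts in the failure proportion. In the time analysis, date it at the restart, with events ahead of censorings at ties. Do not censor non-failures at restart while keeping later dates for failures.

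**Cost.** One SAP paragraph, one extra table row and, with a T47 restart, one cell in Table 4-2; restart dates are already collected. A T47 draw needs a clinic visit or a home draw for subjects who dose at home. The documents do not say whether the first ~300 subjects are past the restart. If they are, their end-of-monotherapy value comes mostly from T42-45, while the third cohort's comes from the new sample; Groups B and C within that cohort stay comparable. Reported week-48 suppression may be slightly lower.

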#### 4.3 VIROLOGIC FAILURE (VF) VISIT

Virologic failure is defined as two consecutive levels of  $\geq 200$  copies/mL.

Subjects in Group A or Group B that experience virologic failure have option of re-initiating ART regimen or participating in Part 2 of Treatment Phase and receive higher dose of PRO 140 weekly injection for remainder of 48-week Treatment Phase or until subsequent virologic failure event after viral re-suppression on higher dose.

The following assessments will be performed for all subjects who experience virologic failure during the Treatment Phase, prior to entering Follow-up Phase:

- Assess for any Adverse Events and changes in Concomitant medications (see [Section 9](#) and [7.5](#)),
- Complete Physical Examination (see [Section 7.6](#)),
- Vital Signs (see [Section 7.9](#)),
- Neurological Assessment (see [Section 7.8](#)),
- Electrocardiogram (ECG) (see [Section 7.7](#))
- Subject-perceived Injection Site Pain Assessment (see [Section 7.13](#)),
- Collection of Blood Specimens (see [Section 7.10](#)) for
  - Plasma HIV-1 RNA level
  - TruCount T Assay

- Complete Blood Count
- Biochemistry
- Coagulation Indices
- HIV Drug Resistance Assay (PhenoSense GT/Integrase)
- HIV Trofile® RNA Assay
- CCR5 Receptor Occupancy (IncellDx Lab)
- Anti-idiotypic antibodies to PRO 140
- PK sample for PRO 140
- Blood sample for evaluation of potential biomarkers [*occurs at T48*]
  - Immune Activation Markers
  - PhenoSense® Entry Assay
  - Quest Diagnostics HIV Co-receptor Tropism Assay
- CSF sample collection for CNS sub-study (see [Section 7.10.16](#))
  - **Note:** *CSF sample should be collected at VF visit for subjects participating in CNS sub-study.*
- Genital secretion sample collection for GU sub-study (see [Section 7.10.17](#))
  - **Note:** *Genital secretion sample should be collected at VF visit for subjects participating in GU sub-study.*
- Collection of Urine Specimen for Urinalysis (see [Section 7.10.15](#))
- Measurement of treatment adherence (see [Section 7.14](#))
- Re-initiate previous antiretroviral regimen or an alternative regimen selected by the treating physician

